6.2 Treatment Regimens

As indicated at the end of [Section 3](#), the current version of this SAP does not consider any randomization nor the DL3B regimen while describing the planned analyses.

The cohorts are defined by the ulocuplumab regimen only. The nivolumab regimen will always be 3mg/kg every 2 weeks (no nivolumab dose modification is allowed).

The cohort “as allocated” will be retrieved from the IVRS.

The cohort “as treated” will be the same as the cohort “as allocated” by IVRS. However, if a subject received an incorrect drug for the entire period of treatment, the subject’s cohort will be defined by the incorrect drug the subject actually received.

For the Dose Evaluation Phase and the 2-stage design, all analysis will be presented “as-treated”.

6.3 Populations for Analyses

All populations will be defined separately by tumor type.

- Dose Evaluation Phase:
 - All DLT-evaluable Subjects: All subjects who completed the DLT evaluation period (i.e., received at least 5 out of 6 doses of ulocuplumab and at least 2 out of 3 doses of nivolumab in a 6 week dosing period or experienced a DLT).
 - All Dose Evaluation Enrolled Subjects: All subjects who signed an informed consent form and were registered into the IVRS during the Dose Evaluation Phase (this population includes subjects from the DLT evaluation period).
 - All Dose Evaluation Treated Subjects: All subjects who received at least one dose of any study medication during the Dose Evaluation Phase (this population includes subjects from the DLT evaluation period).
 - All Dose Evaluation Excluding DLT Treated Subjects: All subjects who were allocated to a unique cohort during the Dose Evaluation Phase and were treated (this population excludes subjects from the DLT evaluation period).
- Dose Expansion Phase:
 - All Dose Expansion Enrolled Subjects: All subjects who signed an informed consent form and were registered into the IVRS during the Dose Expansion Phase.
 - All Dose Expansion Treated Subjects: All subjects who were allocated to a unique cohort during the Dose Expansion Phase and were treated (this population correspond to the second stage of a 2-stage design and it will not be used as such for reporting, see “Both Phases combined” below).
- Both Phases combined:
 - All 2-stage Enrolled Subjects: This population consists of the pooling of the “All Dose Evaluation Enrolled Subjects” with the “All Dose Expansion Enrolled Subjects”.
 - All 2-stage Treated Subjects: This population consists of the pooling of the “All Dose Evaluation Excluding DLT Treated Subjects” with the “All Dose Expansion Treated Subjects”.
 - All 2-stage Including DLT Treated Subjects: This population consists of the pooling of the “All Dose Evaluation Treated Subjects” with the “All Dose Expansion Treated Subjects”.
- Other populations (note that the PK and the immunogenicity are study drug specific as these populations are defined for ulocuplumab or for nivolumab, separately):
 - All Dose Evaluation PK Evaluable Subjects: All subjects who received at least one dose of study medication and have available serum concentration data during the Dose Evaluation Phase.
All Dose Expansion PK Evaluable Subjects: All subjects who received at least one dose of study medication and have available serum concentration data during the Dose Expansion Phase.
 - All Dose Evaluation Biomarker Evaluable Subjects: All subjects who received at least one dose of study medication and have baseline and at least one post-baseline biomarker assessment during the Dose Evaluation Phase.

- All Dose Expansion Biomarker Evaluable Subjects: All subjects who received at least one dose of study medication and have baseline and at least one post-baseline biomarker assessment during the Dose Expansion Phase.
- All Dose Evaluation Immunogenicity Evaluable Subjects: All subjects who received at least one dose of study medication and have baseline and at least one post-baseline immunogenicity assessment during the Dose Evaluation Phase.
- All Dose Expansion Immunogenicity Evaluable Subjects: All subjects who received at least one dose of study medication and have baseline and at least one post-baseline immunogenicity assessment during the Dose Expansion Phase.

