**Randomized Phase 2 (per tumor type):**

### 3.1.1 Dose Evaluation Phase (Stage 1)

The Dose Evaluation Phase will consist of a DLT evaluation period followed by an evaluation of up to three cohorts with various doses and schedules of ulocuplumab combined with nivolumab. The DLT evaluation period will be conducted in the first 3-6 subjects with either PAC or SCLC at dose level 1 (DL1; 400 mg weekly ulocuplumab combined with nivolumab), followed by 3-6 subjects each with PAC and SCLC at DL2 (800 mg weekly ulocuplumab combined with nivolumab), followed by 3-6 subjects each with PAC and SCLC at DL3A (1600 mg weekly ulocuplumab combined with nivolumab) for 6 weeks. For DL1, both tumor types will be combined for the safety evaluation. If 2 or more DLT are observed at DL1, de-escalation to DL-1 will occur (200 mg weekly ulocuplumab combined with nivolumab). For all other dose levels, each tumor type will be evaluated for safety independently in the event that tumor specific AE may emerge.

Enrollment during the DLT evaluation phase will allow for concurrent accrual of up to 6 subjects in each dose/tumor cohort (ie, Rolling Six design). This design allows for 3-6 evaluable subjects to contribute to the DLT evaluation depending upon how many are enrolled and still being evaluated during the DLT period. Decisions as to whether to enroll a new participant onto the current dose level or next highest dose level will be based on available data at the time of new participant enrollment. Study stopping rules for the DLT evaluation period and the decision to proceed with the Dose Evaluation Phase include the following:

- Enrollment in the active cohort will proceed if there are:
  - < 3 subjects enrolled, up to a maximum of 6 subjects
  - 1 DLT in 2 or up to 5 subjects evaluable for toxicity
- Enrollment in the active cohort will be paused if there are:
  - a maximum of 6 subjects enrolled (including evaluable and non-evaluable)
- Active cohort is deemed intolerable and enrollment will be stopped for evaluation if there are:
  - ≥ 2 DLT in up to 6 subjects evaluable for toxicity
- Active cohort is deemed tolerable and enrollment will proceed to next step if there are :
  - 0 DLT in 3 or up to 6 subjects evaluable for toxicity
  - 1 DLT in 6 subjects evaluable for toxicity
- Subjects who are not evaluable for DLT (ie, discontinuation due to disease progression) will be replaced with a concurrently enrolled subject

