**Table 3.1.1-1: Dose Levels for Ulocuplumab and Nivolumab**

Dose Level	Ulocuplumab	Nivolumab
DL-1	200 mg weekly	3 mg/kg every 2 weeks
DL1	400 mg weekly	3 mg/kg every 2 weeks
DL2	800 mg weekly	3 mg/kg every 2 weeks
DL3A	1600 mg weekly	3 mg/kg every 2 weeks

DL3B	1600 mg every 2 weeks	3 mg/kg every 2 weeks
------	-----------------------	-----------------------

Depending on the number of DLT observed during the DLT evaluation period, escalation or de-escalation of ulocuplumab may be warranted. Dose escalation/de-escalation at the 800 mg weekly and 1600 mg weekly ulocuplumab dose levels will occur independently for each tumor type. No dose modification of nivolumab will be allowed in this study.

- If the toxicity at DL1 and DL2 and DL3A are acceptable, enrollment will proceed with three randomized cohorts (DL2, DL3A, and DL3B) to complete Stage 1
- If the toxicity at DL3A is unacceptable, enrollment will proceed at DL2 to complete Stage 1
- If the toxicity at DL2 is unacceptable, enrollment will proceed at DL1 to complete Stage 1
- If the toxicity at DL1 is unacceptable, a new DLT evaluation period will proceed at DL-1
- If the toxicity of DL-1 is unacceptable, enrollment will stop for that tumor type
- If the toxicity at DL-1 is acceptable, enrollment will proceed at DL-1 to complete Stage 1 at a single dose level

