### **3.1.4 Dose Limiting Toxicity**

The incidence of DLT(s) assessed in the first 3-6 evaluable subjects per tumor type (if applicable) during the first 6 weeks will be used to initially determine whether a dose level is tolerable. A subject will be considered evaluable for DLT if they have received at least 5 out of 6 ulocuplumab doses and at least 2 out of 3 nivolumab doses in a 6 week dosing period or experienced a DLT. DLT should not be AE considered by the investigator to be disease related. The following drug-related AE (whether related to one or both agents) will be considered a DLT:

- Any Grade  $\geq 3$  drug-related non-hematological AE, including the following laboratory abnormalities
  - If a subject has baseline Grade  $\leq 1$  AST, ALT, or total bilirubin, a drug-related Grade  $\geq 3$  toxicity will be considered a DLT
  - If a subject has baseline Grade 2 AST or ALT, drug-related elevations in AST and/or ALT  $> 2x$  baseline or a maximum of  $> 8x$  ULN will be considered a DLT
- Any Grade 4 drug-related hematological AE or hematological or non-hematological laboratory abnormality with the following exceptions:
  - Grade 4 amylase or lipase not associated with symptoms or clinical manifestations
  - Grade 4 lymphocytopenia not associated with symptoms or clinical manifestations
- Any drug-related AE that results in dose reduction of ulocuplumab during the DLT period
- Any drug related AE that results in dose delay of ulocuplumab  $> 14$  days during DLT period
- Any toxicity managed by discontinuation of ulocuplumab (see [section 4.5.3.1](#))
- Any toxicity managed by discontinuation of nivolumab (see [section 4.5.3.2](#))

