**Table 4.5.2.1-1: Ulocuplumab Dose Modification Criteria**

Adverse Event	Dose Delay (refer to section 4.5.1.1)	Criteria to Resume Ulocuplumab Treatment			
		For DL-1	For DL1	For DL2	For DL3A/3B
Any Gr ≥ 3 drug-related AE, including laboratory abnormalities, except for Grade 3 hematologic AEs listed below or other exceptions listed in section 4.5.1	Hold ulocuplumab until return to baseline or Grade ≤ 1, whichever is lower	1st event: Discontinue ulocuplumab	1st event: Resume at 200 mg weekly	1st event: Resume at 400 mg weekly	1st event: Resume at 800 mg weekly
			2nd event: Discontinue ulocuplumab	2nd event: Resume at 200 mg weekly	2nd event: Resume at 400 mg weekly
				3rd event: Discontinue ulocuplumab	3rd event: Discontinue ulocuplumab
Any Gr3 drug-related neutropenia, Gr3 thrombocytopenia > 7 days	Hold ulocuplumab until return to baseline or Grade ≤ 1, whichever is lower	2nd event: Discontinue ulocuplumab	1st event: Resume at 200 mg weekly	1st event: Resume at 400 mg weekly	1st event: Resume at 800 mg weekly
			3rd event: Discontinue ulocuplumab	2nd event: Resume at 200 mg weekly	2nd event: Resume at 400 mg weekly
				3rd event: Discontinue ulocuplumab	3rd event: Discontinue ulocuplumab
Gr4 asymptomatic lipase or amylase elevations	Hold ulocuplumab until return to baseline or Grade ≤ 1, whichever is lower	All events: Resume at same dose. Consult with BMS Medical Monitor if recurrent or sustained.			

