2.1.1 Dose Evaluation Phase (Stage 1)

The Dose Evaluation Phase will consist of a DLT evaluation period followed by an evaluation of up to three cohorts with various doses and schedules of ulocuplumab combined with nivolumab. The DLT evaluation period will be conducted in the first 3-6 subjects with either PAC or SCLC at dose level 1 (DL1; 400 mg weekly ulocuplumab combined with nivolumab), followed by 3-6 subjects each with PAC and SCLC at DL2 (800 mg weekly ulocuplumab combined with nivolumab), followed by 3-6 subjects each with PAC and SCLC at DL3A (1600 mg weekly ulocuplumab combined with nivolumab) for 6 weeks. For DL1, both tumor types will be combined for the safety evaluation. If 2 or more DLT are observed at DL1, de-escalation to DL-1 will occur (200 mg weekly ulocuplumab combined with nivolumab). For all other dose levels, each tumor

type will be evaluated for safety independently in the event that tumor specific AE may emerge. Enrollment during the DLT evaluation phase will allow for concurrent accrual of up to 6 subjects in each dose/tumor cohort (i.e., Rolling Six design¹).

The incidence of DLT(s) assessed during the first 6 weeks of treatment will be used to initially determine whether a dose level is tolerable. DLT should not be adverse event (AE) considered by the investigator to be disease related. The following drug-related AE (whether related to one or both agents) will be considered a DLT:

- Any drug-related non-hematological AE of Grade ≥ 3 , including the following laboratory abnormalities:
 - If a subject has baseline Grade ≤ 1 AST, ALT, or total bilirubin, a drug-related Grade ≥ 3 toxicity will be considered a DLT
 - If a subject has baseline Grade 2 AST or ALT, drug-related elevations in AST and/or ALT $> 2x$ baseline or a maximum of $> 8x$ ULN will be considered a DLT
- Any Grade 4 drug-related hematological AE or hematological or non-hematological laboratory abnormality with the following exceptions:
 - Grade 4 amylase or lipase not associated with symptoms or clinical manifestations
 - Grade 4 lymphocytopenia not associated with symptoms or clinical manifestations
- Any drug-related AE that results in dose reduction of ulocuplumab during the DLT period
- Any drug related AE that results in dose delay of ulocuplumab > 14 days during DLT period
- Any toxicity managed by discontinuation of ulocuplumab or nivolumab.

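### A subject who misses two of six weekly ulocuplumab doses through drug toxicity can be neither a DLT nor DLT-evaluable, so a dose level can clear on three other subjects

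*SAP*

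**What the plan says.** **Evaluability.** Protocol 3.1.4 calls a subject evaluable if they "received at least 5 out of 6 ulocuplumab doses and at least 2 out of 3 nivolumab doses" in the six-week period, or had a DLT. Protocol 8.2 repeats the rule, and so does SAP 6.3, where the subject must have "received at least 5 out of 6 doses of ulocuplumab and at least 2 out of 3 doses of nivolumab" or had a DLT.

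**Holds as DLTs.** Protocol 3.1.4 and SAP 2.1.1 list "Any drug related AE that results in dose delay of ulocuplumab > 14 days during DLT period". Toxicity that leads to a ulocuplumab dose reduction, or to stopping either drug, is also a DLT. Skipped doses are not made up (Protocol 4.5.1.1 and 4.5.1.2).

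**Clearing a level.** Under Protocol 3.1.1 a level is tolerable with "0 DLT in 3 or up to 6 subjects evaluable for toxicity", or with one DLT in six. Two or more DLTs make it intolerable. Enrollment pauses at six subjects, and non-evaluable subjects count towards the six. On replacement the text is: "Subjects who are not evaluable for DLT (ie, discontinuation due to disease progression) will be replaced with a concurrently enrolled subject".

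**What follows at DL-1.** SAP 2 reports more than two DLTs at DL1 and says that DL-1 (200 mg weekly), the lowest level, has been opened. The protocol then says: "If the toxicity at DL-1 is acceptable, enrollment will proceed at DL-1 to complete Stage 1 at a single dose level". That means 19 SCLC or 21 PAC subjects (SAP 5.1 and 5.2).

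**Other safety data.** Protocol 8.4.3 requires all available safety and tolerability data to be used in the DLT phase. SAP 7.6.1 says that other data may be considered.

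**The concern.** The dose-count rule and the delay rule do not meet. Two missed weekly doses are enough to lose evaluability but, on schedule, not enough to be a DLT by delay. When the doses were missed because of the drugs, the exclusion is informative: the subject leaves the numerator and the denominator because the regimen was not tolerated.

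Ordinary management rules can produce this. Under Protocol 4.5.1.2 most Grade 2 non-skin drug-related events (fatigue and laboratory findings apart) hold nivolumab. Ulocuplumab should then be held too, and nivolumab restarts at its next scheduled visit. Grade 4 lipase or amylase elevation without symptoms is a second route: it is exempt from the DLT list, but Table 4.5.2.1-1 holds ulocuplumab for it.

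The rolling-six gate is a small count, so one or two such exclusions can matter. It decides whether the lowest dose level goes forward.

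**Working it through.** The documents give no operating characteristic for the DLT rule, so there is no plan figure to reproduce.

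**1. Missed-dose patterns.** Ulocuplumab is due on Days 1, 8, 15, 22, 29 and 36, and next on Day 43. Protocol 3.1.4 does not say how a delay is measured. I used SAP 7.4.2.2: days since the previous dose minus 7. Dose 1 is taken as given.

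| Doses missed (of 2–6) | Patterns | Longest delay | DLT by delay | Evaluable without a DLT |
|---|---|---|---|---|
| 1 | 5 | 7 days | 0 | 5 |
| 2 | 10 | 14 days (4 consecutive pairs), 7 days (6 separated pairs) | 0 | 0 |
| 3 | 10 | 21 days (3 consecutive triples), 7 or 14 days (the other 7) | 3 | 0 |

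All 10 two-dose patterns, and 7 of the 10 three-dose patterns, fall in the gap.

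**2. Worked case.** A Grade 2 event holds both drugs from Day 15 to Day 29.
- Nivolumab is given on Days 1 and 29: 2 of 3.
- Ulocuplumab is given on Days 1, 8, 29 and 36: 4 of 6.
- The delay is (29 − 8) − 7 = 14 days, which is not more than 14.

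The subject is neither a DLT nor evaluable. With the ±1 day dosing window, a restart on Day 28, 29 or 30 gives 13, 14 or 15 days, and only Day 30 makes it a DLT.

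**3. Effect on a cohort.** Three clean subjects and two with such holds count as 0 DLT in 3, which clears. If the two holds counted as DLTs, the result would be 2 in 5, which is intolerable. Only five subjects are enrolled, so the pause at six does not intervene.

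**4. Chance of clearing with six enrolled.** Let d be the DLT rate, h the rate of toxicity holds in the gap, and n = 1 − d − h. Both d and h are assumptions.
- As written (no DLT with at least 3 evaluable, or 1 DLT with 6 evaluable): n⁶ + 6hn⁵ + 15h²n⁴ + 20h³n³ + 6dn⁵.
- Holds counted as DLTs (at most one event in six): n⁶ + 6(d + h)n⁵.
- Difference: 15h²n⁴ + 20h³n³, the chance of clearing with two or three subjects removed by toxicity.

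For d = 0.10 and h = 0.10, n = 0.80:
- As written: 0.2621 + 0.1966 + 0.0614 + 0.0102 + 0.1966 = 0.727.
- Holds counted: 0.2621 + 0.3932 = 0.655.

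| d | h | As written | Holds counted | Difference |
|---|---|---|---|---|
| 0.10 | 0.05 | 0.798 | 0.776 | 0.021 |
| 0.10 | 0.10 | 0.727 | 0.655 | 0.072 |
| 0.10 | 0.20 | 0.619 | 0.420 | 0.199 |
| 0.05 | 0.10 | 0.867 | 0.776 | 0.091 |
| 0.05 | 0.20 | 0.791 | 0.534 | 0.257 |
| 0.20 | 0.10 | 0.463 | 0.420 | 0.043 |
| 0.20 | 0.20 | 0.346 | 0.233 | 0.112 |

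A cohort left at the pause without meeting the clearing rule, such as one DLT, one hold and four clean subjects, is treated as not cleared.

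**The case against.** **Serious toxicity is still caught.** This stands. Grade 3 or higher non-hematologic events, Grade 4 events outside the exemptions, discontinuations and delays over 14 days are all DLTs. The gap holds only what is left.

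**The count is not the whole decision.** Protocol 3.1.4 says DLT incidence determines tolerability initially. Protocol 7 requires regular safety calls, Protocol 8.4.3 requires use of all safety data, and SAP 7.6.1 requires the reasoning to be described. SAP 7.2.1 already tabulates enrolled, treated and DLT-evaluable numbers. These are real safeguards, but none says how a toxicity-related shortfall enters the count.

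**The threshold may be deliberate.** The DLT criteria were revised in Amendments 03 and 04, and the current text uses more than 14 days. Making every two-week hold for a Grade 2 event a DLT would be a stricter definition, and that is the sponsor's choice. It does not explain why such subjects should leave the denominator.

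Three stronger readings are tempting and are not supported:
- *Toxicity cases are replaced without limit.* Unlimited replacement would give 90%, 89% and 86% as written against 81%, 71% and 49%, at hold rates of 5%, 10% and 20% and a 10% DLT rate. That ignores the pause at six, which includes non-evaluable subjects. The replacement sentence also uses ie before disease progression, so replacement after a toxicity hold is only one reading. The gap does not need it, because no DLT in three still clears.
- *The same Grade 3 hematologic event counts at 400 mg but not at 200 mg.* The row "Any Gr3 drug-related neutropenia, Gr3 thrombocytopenia > 7 days" in Table 4.5.2.1-1 suggests this: DL1 resumes at 200 mg, a reduction and so a DLT, while the DL-1 cell shows discontinuation only at the second event. But the row is incomplete in the available text: DL-1 has no first event and DL1 goes from first to third. The asymmetry is possible, not shown. SAP 2 also reports no ulocuplumab dose reduction at DL1.
- *All ten two-dose patterns are equally likely.* The six separated pairs may need two holds. A single continuous hold gives the four consecutive pairs, at exactly 14 days.

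**Conclusion.** The concern holds as a gap in the counting rule. Two ulocuplumab doses missed through a drug-related event that is not otherwise a DLT make a subject neither an event nor evaluable, and the level can clear on three others. This follows from the text, given on-schedule dosing and the SAP's measure of delay.

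Its size depends on a hold rate that the documents do not give. At a 10% DLT rate with six enrolled, the difference from counting such holds as DLTs is about 2, 7 and 20 percentage points at hold rates of 5%, 10% and 20%. It is small if such holds are rare and material if about one subject in five has one. The comparison measures what the exclusion can hide; it does not show that counting every hold as a DLT is the correct rule. The point should be settled before DL-1 is judged tolerable.

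**What to change.** 1. In Protocol 3.1.1 and 3.1.4 (with 8.2) and SAP 6.3, state that only subjects who fall short of the dose count for reasons that are not drug-related are non-evaluable and replaceable.
2. In SAP 7.6.1, list by dose level the DLT-period subjects who fell short because of a drug-related event. Report DLT incidence both as defined and with these subjects counted as events, before DL-1 is called tolerable.
3. As an option for the sponsor, make two or more ulocuplumab doses missed through a drug-related event a DLT.

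Items 1 and 2 belong together. Item 1 alone keeps these subjects in the denominator as non-events and does not make clearing harder: at d = 0.10, at most one DLT in six evaluable subjects has probability 0.9⁶ + 6 × 0.1 × 0.9⁵ = 0.886. The second count in item 2 supplies the caution. If the protocol is not amended, item 2 can be done in the SAP alone.

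The cost is one sentence, carried through the matching sections, and one table row, with a slightly more conservative tolerability call. No new data are needed: SAP 7.4.2.2 already summarizes dose delays with reasons, and SAP 7.6.5 summarizes adverse events that lead to delay.

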7 STATISTICAL ANALYSES

7.1 General Methods

All analyses will be presented separately by tumor type.

Descriptive summaries of continuous and other numeric variables will at least consist of the following summary statistics: median, minimum and maximum values. Categorical variables will be summarized by the frequency and proportion of subjects falling into each category. Unless otherwise indicated, percentages in tables will be column percentages, using the total number of observations in the population, grouped by cohort, as the denominator. Percentages will be rounded to one decimal place, and thus may not always add up to exactly 100%.

AEs will be coded using the Medical Dictionary for Regulatory Activities (MedDRA), and the most recent version of the dictionary at the time of the database lock will be used. AEs and laboratory tests will be graded using the National Cancer Institute - Common Toxicity Criteria for Adverse Event (NCI-CTCAE) Version 4.03. Clinical laboratory values will be first reported in using International System of Units (SI). Analyses will be repeated using US conventional units. Medications will be coded using the most recent version of the BMS WHO Drug Dictionary.

Time-to event variables (e.g., PFS, OS, DOR, etc.) will be analyzed using the Kaplan-Meier product limit method (KM). When specified, the median will be reported along with 95% confidence interval (CI) using Brookmeyer and Crowley methodology⁴ (using the log-log transformation for construction of CI). Rates at fixed timepoints (e.g., PFS at 6 months) will be derived from the Kaplan-Meier estimate along with their corresponding log-log transformed CIs. Exact confidence intervals for binomial proportions will be derived using the Clopper-Pearson method⁵.

